# 7 SAFETY MONITORING AND REPORTING

#### 7.1 Overview

This section defines the types of safety data that will be collected under this protocol and outlines the procedures for appropriately collecting, grading, recording, and reporting that data. Adverse events that are classified as serious according to the definition of health authorities must be reported promptly (per Section 7.5, *Reporting of Adverse Events*) and appropriately to the sponsor (DAIT/NIAID), principal investigators in the trial, and Institutional Review Boards (IRBs). Information in this section complies with *ICH Guideline E2A: Clinical Safety Data Management: Definitions and Standards for Expedited Reporting, ICH Guideline E-6: Guideline for Good Clinical Practice,* and applies the standards set forth in the National Cancer Institute (NCI), *Common Terminology Criteria for Adverse Events (CTCAE), Version 4.0*: http://ctep.cancer.gov/reporting/ctc.html.

#### 7.2 **Definitions**

#### 7.2.1 Adverse Event (or Adverse Experience)

Any untoward or unfavorable medical occurrence in a human subject, including any abnormal sign, symptom, or disease, temporally associated with the subject's participation in the research, whether or not considered related to the subject's participation in the research (modified from the definition of adverse events in the 1996 International Conference on Harmonization E-6 Guidelines for Good Clinical Practice)." [From OHRP "Guidance on Reviewing and Reporting Unanticipated Problems Involving Risks to Subjects or Others and Adverse Events (1/15/07)" <http://www.hhs.gov/ohrp/policy/AdvEvntGuid.htm>

#### 7.2.2 Adverse Reaction and Suspected Adverse Reaction

An adverse reaction means any adverse event caused by a drug. Adverse reactions are a subset of all suspected adverse reactions for which there is reason to conclude that the drug caused the event.

Suspected adverse reaction (SAR) means any adverse event for which there is a reasonable possibility that the drug caused the adverse event. For the purposes of safety reporting, 'reasonable possibility' means there is evidence to suggest a causal relationship between the drug and the adverse event. A suspected adverse reaction implies a lesser degree of certainty about causality than adverse reaction, which means any adverse event caused by a drug (21 CFR 312.32(a)).

#### 7.2.3 Unexpected Adverse Reaction

A SAR is considered "unexpected" if it is not listed in the MMF package insert or is not listed at the specificity or severity that has been observed.

#### 7.2.4 Serious Adverse Event

An AE or SAR is considered "serious" if, in the view of either the investigator or DAIT/NIAID, it results in any of the following outcomes (21 CFR 312.32(a)):

- 1. Death
- 2. A life-threatening event: An AE or SAR is considered "life-threatening" if, in the view of either the investigator or DAIT/NIAID, its occurrence places the subject at immediate risk of death. It does not include an AE or SAR that, had it occurred in a more severe form, might have caused death.
- 3. Inpatient hospitalization or prolongation of existing hospitalization
- 4. Persistent or significant incapacity or substantial disruption of the ability to conduct normal life functions
- 5. Congenital anomaly or birth defect

Important medical events that may not result in death, be life threatening, or require hospitalization may be considered serious when, based upon appropriate medical judgment, they may jeopardize the subject and may require medical or surgical intervention to prevent one of the outcomes listed above.

#### 7.3 Collection and Recording of Adverse Events

#### 7.3.1 **Investigational Product**

The primary investigational product in this protocol is MMF. In addition, subjects in this protocol are required to receive hydroxychloroquine or chloroquine. For purposes of reporting safety information, these drugs will be considered concurrent study mandated therapy.

#### 7.3.2 **Collection Period**

Adverse events will be collected from the time the subject signs the informed consent until he/she initiates study intervention or until he/she is determined to be ineligible to receive study intervention, if the investigator determines that the adverse event is related to a study-mandated procedure, treatment, or change in treatment.

Regardless of whether the above is applicable, for all participants: Adverse events will be collected from the time of initiation of study intervention (i.e., the administration of the first dose of study-supplied MMF as defined in Section 6.4.2, *Baseline/Randomization Visit*) until he/she completes study participation or until 30 days after he/she prematurely withdraws (without withdrawing consent) or is withdrawn from the study.

#### 7.3.3 Collecting Adverse Events

Adverse events (including SAEs) may be discovered through any of these methods:

• Observing the subject.

- Questioning the subject in an objective manner.
- Receiving an unsolicited complaint from the subject.
- In addition, an abnormal value or result from a clinical or laboratory evaluation (including, but not limited to, a radiograph, an ultrasound, or an electrocardiogram) can also indicate an adverse event, as defined in Section 7.4, *Grading and Attribution of Adverse Events*.

#### 7.3.4 **Recording Adverse Events**

Throughout the study, the investigator will record and grade adverse events NCI-CTCAE grade 2 and above on the appropriate AE electronic case report form (AE eCRF) regardless of their severity or relation to study medication or study procedure.

Once recorded, an AE will be followed until it resolves with or without sequelae, or until the end of study participation, or until 30 days after the subject prematurely withdraws (without withdrawing consent)/or is withdrawn from the study, whichever occurs first.

#### 7.3.5 **Recording Serious Adverse Events**

Serious AEs will be recorded on the appropriate AE eCRF and on the SAE eCRF. All requested information on the AE eCRF and SAE eCRF should be provided, if available, for submission to the Statistical and Clinical Coordinating Center (SACCC) and DAIT/NIAID.

If a site investigator discovers a new serious adverse event within 30 days after the end of study participation, the SAE will be reported.

Once recorded, an SAE will be followed until it resolves with or without sequelae.

#### 7.4 Grading and Attribution of Adverse Events

#### 7.4.1 **Grading Criteria**

The study site will grade the severity of adverse events experienced by the study subjects according to the criteria set forth in the National Cancer Institute's *Common Terminology Criteria for Adverse Events Version (CTCAE)* 4.0. This document (referred to herein as the NCI-CTCAE manual) provides a common language to describe levels of severity, to analyze and interpret data, and to articulate the clinical significance of all adverse events. The NCI-CTCAE has been reviewed by the Protocol Chair(s) and has been deemed appropriate for the subject population to be studied in this protocol.

Adverse events will be graded on a scale from 1 to 5 according to the following standards in the NCI-CTCAE manual:

Grade 1 = mild adverse event, not recorded.

Grade 2 = moderate adverse event.

Grade 3 = severe and undesirable adverse event.

Grade 4 = life-threatening or disabling adverse event.

Grade 5 = death.

If NCI-CTCAE criteria are defined for grading an abnormal value or result from a clinical or laboratory evaluation (including, but not limited to, a radiograph, an ultrasound, or an electrocardiogram), then a treatment-emergent adverse event is defined as an increase in grade from Baseline (Day 0) or from the last post-baseline value that doesn't meet grading criteria. Changes in grade from screening to Baseline (Day 0) will also be recorded as outlined in Section 7.3.2, *Collection Period*. If a specific event or result from a given clinical or laboratory evaluation is not included in the NCI-CTCAE manual, then an abnormal result would be considered an adverse event if changes in therapy or monitoring are implemented.

Adverse events that are related to disease activity will be graded according to the plan outlined above. However, an increase in disease activity leading to an adverse event should also be reflected in standard measures of disease activity (BILAG\* 2004 and SELENA-SLEDAI) measured at regularly scheduled visits as well as at flare and endpoint visits.

To facilitate identification of a safety signal associated with increased disease activity, the modified BILAG\* 2004 and SELENA-SLEDAI\* tools will be used throughout the study to monitor changes in disease activity over time. The DSMB will receive reports on these assessments for each treatment arm at regularly scheduled reviews.

#### 7.4.2 **Attribution Definitions**

The relation, or attribution, of an adverse event to an investigational product will initially be determined by the site investigator. The site investigator will also record the initial determination of attribution on the appropriate AE eCRF. The relation of an adverse event to the study intervention will be determined using the descriptors and definitions provided in Table 7.1, *NCI-CTCAE attribution of adverse events*. Final determination of attribution for safety reporting will be decided by DAIT/NIAID.

For additional information and a printable version of the NCI-CTCAE manual, consult the NCI-CTCAE web site: http://ctep.cancer.gov/reporting/ctc.html.

Code	Descriptor	Relationship (to primary investigational product and/or other concurrent mandated study therapy)				
Unrelate	Unrelated Categories					
1	Unrelated	The adverse event is clearly not related.				
2	Unlikely	The adverse event is unlikely related.				
Related	Related Categories					
3	Possible	The adverse event has a reasonable possibility to be related; there is evidence to suggest a causal relationship.				
4	Probable	The adverse event is likely related.				
5	Definite	The adverse event is clearly related.				

#### Table 7.1NCI-CTCAE attribution of adverse events

#### 7.5 Reporting of Adverse Events

#### 7.5.1 **Reporting of Adverse Events to DAIT/NIAID**

This section describes the responsibilities of the site investigator to report adverse events to the SACCC. Timely reporting of adverse events is required by 21 CFR and ICH E6 guidelines. For this study, adverse events of NCI-CTCAE Grade 2 and higher will be reported.

#### 7.5.1.1 **Procedure for Adverse Events Requiring 24 Hour Reporting**

The adverse events that are bulleted below must be reported by site investigators to the SACCC regardless of relationship or expectedness to study intervention within a 24 hour period of discovering the adverse event:

- All SAEs per 21 CFR 312.32 definitions (see Section 7.2.4, Serious Adverse Event).
- All BILAG\* A flares.
- All severe SELENA-SLEDAI\* flares.

Elective hospitalizations or hospital admissions for the purpose of conduct of protocolmandated procedures are not to be reported as an SAE unless hospitalization is prolonged due to complications.

The following process for reporting of the adverse events bulleted above ensures compliance with the ICH guidelines and the Food and Drug Administration (FDA) CFR regulations. When an investigator identifies such an adverse event, he or she must notify the SACCC within 24 hours of discovering the adverse event, and complete and submit the AE/SAE eCRF within one business day following initial notification. The SACCC is responsible for notifying DAIT/NIAID upon receipt of the site's notification of the adverse event and sending a SAE report form to DAIT/NIAID within two business days after receipt of the AE/SAE eCRF from the site.

#### 7.5.1.2 **Procedure for Standard Adverse Event Reporting**

All other adverse events (Section 7.3.3, *Collecting Adverse Events*) must be recorded by the site on the appropriate AE eCRF within five business days of the site learning of the adverse event(s).

BILAG\* A and severe SELENA-SLEDAI\* flares will be reported as described above in Section 7.5.1.1, *Procedure for Adverse Events Requiring 24 Hour Reporting*; all other BILAG\* and SELENA-SLEDAI\* flares will be reported using standard AE reporting timelines.

# 7.5.2 **DAIT/NIAID Reporting to the Health Authority**

This clinical study has been granted exemption from IND regulations by the FDA in accordance with 21 CFR 312.2(b) of the regulations, therefore, AEs will not be reported to the FDA by the study sponsor (NIAID).

# 7.5.3 **Reporting of Adverse Events to IRBs**

All investigators must report adverse events in a timely fashion to their respective IRBs in accordance with applicable regulations and local reporting guidelines.

# 7.6 Pregnancy Reporting

This study includes pregnancy information as safety data. Information about any pregnancy should be reported promptly to the SACCC on the same timeline as an SAE (Section 7.5.1.1, *Procedure for Adverse Events Requiring 24 Hour Reporting*).

All pregnancies identified during the study must be followed to conclusion and the outcome of each must be reported. The investigator should be informed immediately of any pregnancy in a study subject or a partner of a study subject. A pregnant subject should be instructed to stop taking study medication. The investigator should report to the SACCC all pregnancies within 1 business day (as described in Section 7.5.1.1, *Procedure for Adverse Events Requiring 24 Hour Reporting*) using the Pregnancy eCRF. The investigator should counsel the subject and discuss the risks of continuing with the pregnancy and the possible effects on the fetus. Monitoring of the pregnancy eCRF detailing the outcome of the pregnancy should be submitted to the SACCC. When possible, similar information should be obtained for a pregnancy occurring in a partner of a study subject.

Information requested about the delivery will include:

- Subject's enrollment ID
- Gestational age at delivery
- Birth weight, length, and head circumference
- Gender
- Appearance, pulse, grimace, activity, and respiration (APGAR) score at one minute, five minutes, and 24 hours after birth, if available

• Any abnormalities

Should the pregnancy result in a congenital abnormality or birth defect, an SAE must be submitted to the SACCC using the SAE reporting procedures described above.

#### 7.6.1 Mycophenolate REMS Program

ALE06 investigators are required to enroll in the FDA's Mycophenolate Risk Evaluation and Mitigation Strategy (REMS) program (www.mycophenolaterems.com). An investigator will be required to report any pregnancy occurring in an ALE06 female subject while she is taking MMF or within the first 6 weeks following discontinuation of MMF treatment to the Mycophenolate Pregnancy Registry, which is part of the MMF REMS program. Subjects will be encouraged to participate in MMF REMS program as well.

# 7.7 Reporting of Other Safety Information

An investigator should promptly notify the SACCC when an "unanticipated problem involving risks to subjects or others" is identified, which is not otherwise reportable as an adverse event.

# 7.8 Review of Safety Information

#### 7.8.1 Medical Monitor Review

The DAIT Medical Monitor will receive monthly reports from the SACCC compiling new and accumulating information on AEs, SAEs, and pregnancies recorded by the sites on appropriate eCRFs.

In addition, the Medical Monitor will receive SAE and pregnancy reports for review and triage after the SACCC is made aware of these events (see Sections 7.5.1, *Reporting of Adverse Events to DAIT/NIAID*, and 7.6, *Pregnancy Reporting*).

#### 7.8.2 **DSMB Review**

The Data and Safety Monitoring Board (DSMB) will review accumulating safety data at least yearly during planned DSMB Data Review Meetings. Data for the planned safety reviews will include, at a minimum, a listing of all reported AEs and SAEs. To ensure patient safety between Data Review Meetings, the DSMB will be informed of all Expedited Safety Reports in a timely manner.

In addition to the pre-scheduled data reviews and planned safety monitoring, the DSMB may be called upon for ad hoc reviews or emergency meetings (see Section 5.10.3, *Safety Stopping Guidance*). The DSMB will have discretion to recommend actions regarding study conduct and continuation as a consequence of any planned or unplanned monitoring activity.

# 8 STATISTICAL CONSIDERATIONS AND ANALYTICAL PLAN

#### 8.1 Sample Size and Power

Sample size justification will focus on the primary endpoint of disease reactivation by Week 60. We anticipate that the risk of disease reactivation will likely increase with MMF withdrawal, and recognize that the acceptable level of increased risk will be highly variable among clinicians and their patients. The planned analyses are designed to provide information to help clinicians make decisions for individual patients with varied levels of risk tolerance. To this end, we will provide the estimated risk of disease reactivation in each arm, but more importantly we will provide the % confidence that the increased risk with MMF withdrawal  $\leq a$ , where a is a specific value for acceptable increase in risk. To facilitate decisions for individual patients, we will provide a table and/or plot showing the confidence levels over a range of values for a.

In deriving an appropriate sample size, we assumed most physicians would want at least 85% confidence that the increase in risk with MMF withdrawal  $\leq a$ , for whatever value of a is selected for an individual patient. As such, we computed, under a variety of scenarios, the probability that the study would yield estimates where the confidence was at least 85% that the increase in risk with MMF withdrawal  $\leq a$  (the acceptable increase in risk). Since this probability is analogous to power for a study designed to test a hypothesis, the term "power" will be used in this discussion.

In addition to the study size and the selected value of *a*, power depends on two unknowns: the risk of disease reactivation for patients in the MMF maintenance arm and the increase in risk for patients upon withdrawal of MMF. With respect to the former, a preliminary analysis was conducted on observational data from a subset of 49 patients in the Johns Hopkins Lupus Cohort who were on MMF for a minimum of one year. Based on these results, the probability of experiencing disease reactivation (defined for the preliminary analysis as at least one SELENA-SLEDAI-defined flare requiring additional treatment) by month 16 was estimated at 0.10 (95% CI 0.02-0.19) for subjects remaining on MMF. For the sample size and power calculations, we assumed the risk of disease reactivation in the MMF maintenance arm would be on the range of 0.05 to 0.15. There is no preliminary data on the increase in risk with MMF withdrawal, but since patients/clinicians would be more likely to consider withdrawal if the increased risk were low, we evaluated potential increases ranging from 0.05 to 0.15.

Table 8.1 presents power estimates based on simulations for a sample size of 120 eligible subjects randomized in a 1:1 to MMF maintenance or withdrawal. If all other factors are constant, power improves as **a**, the acceptable level of increased risk, increases. However, the relevance of the study results in clinical practice decreases with increasing **a**. For example, the statement, "We are 85% confident that the increased risk with withdrawal of MMF is < a = 0.20" would be useful for those patients willing to accept an increase in risk of **a**  $\ge 0.20$ , but would not be of value for a more risk-averse patient willing to accept, say, an increase in risk of only **a** = 0.10. Unfortunately, the sample size required to achieve 80%

power when  $\boldsymbol{a} = 0.10$  (or below) are not feasible for this study. For example, if  $\boldsymbol{a} = 0.10$ , then under a best case scenario, if the risk of flare is 0.05 in the MMF maintenance arm and the increase in risk with withdrawal is 0.05 (i.e. the risk with MMF withdrawal = 0.10), then the number of patients required for 80% power is 390.

The sample size of 120 was selected to achieve reasonable power for values of  $a \ge 0.15$ . The study will have the best chance of impacting a wide range of patients if both the risk of disease reactivation in the MMF maintenance arm and the increased risk with withdrawal are low. Table 8.1 shows that if the risk in the MMF maintenance arm is 0.05 and the increase in risk with withdrawal is 0.05, then there is a least 85% power for  $a \ge 0.15$ . If either the risk in the MMF maintenance arm or the increase in risk with withdrawal is larger than 0.05, then the acceptable increase in risk (a) will have to be  $\ge 0.20$  in order to maintain power above 80%.

#### Table 8.1: Power results for 120 subjects (1:1 MMF maintenance: MMF withdrawal)

Risk in the MMF maintenance	Increase in risk with MMF				
arm	withdrawal	0.15	0.2	0.25	0.3
0.05	0.05	85%	98%	100%	100%
0.05	0.10	45%	79%	96%	100%
0.05	0.15		42%	74%	93%
0.15	0.05	66%	87%	97%	99%
0.15	0.10	36%	63%	85%	96%
0.15	0.15		35%	61%	83%

Power = the probability that a random sample will yield estimates with at least 85% confidence that the increase in risk with MMF withdrawal  $\leq a$ 

#### 8.2 Analysis Populations

#### 8.2.1 Safety Population

The safety population (SP), which will be used for all safety analysis, will include all subjects for whom study intervention is initiated.

#### 8.2.2 Modified Intent-to-Treat Population

The modified Intent-to-Treat (mITT) population will include all randomized subjects who begin ALE06-provided MMF and meet study entry criteria. Randomized subjects who withdraw from the trial prior to starting ALE06-provided MMF will be excluded from the mITT analysis set. The analyses for disease activity endpoints will be based on the mITT

population. Subjects who, for whatever reason, do not complete their assigned therapy will be included in the mITT population in the groups to which they were randomized.

#### 8.2.3 **Per Protocol Population**

The Per Protocol (PP) population will be defined as those subjects who adequately comply with the assigned treatment protocol with no serious protocol deviations impacting the primary disease reactivation endpoint or mechanistic outcomes of the study. A masked data review panel will evaluate deviations from the protocol including, for example, departures from assigned treatment regimen, modification of concurrent therapy, failure to complete study visits, or administration of study procedures outside the specified visit windows to determine if occurrence of these deviations should exclude subjects from the PP population. The panel may exclude subjects with serious protocol deviations from the PP population.

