#### 6.4.4 As Needed Visits

#### 6.4.4.1 Flare Visit

A flare visit is to occur when a subject experiences a flare and may coincide with a regularly scheduled or unscheduled study visit.

- FACIT
- SF-36®
- Lupus  $QoL^{\mathbb{C}}$
- Physical examination
- Vitals, including weight
- Physician's global assessment
- SELENA-SLEDAI\*
- SLICC/DI\*
- BILAG\*
- Medications assessment
- AE assessment
- Chemistries (albumin, ALP, ALT, AST, BUN, creatinine, glucose, phosphorus, potassium, bilirubin, total protein)
- Anti-dsDNA, C3, C4
- Hematologies (hemoglobin, MCV, platelet count, RDW, WBC, lymphocytes, monocytes, neutrophils)
- Urinalysis including dipstick, microscopic analysis, spot protein/creatinine

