# Collect the following specimens prior to beginning or increasing treatment with an increased dose of prednisone or immunomodulatory medications.

- Serum for Cytokines/Chemokines/Antibodies to Sm, RNP, SSA/Ro, SSB/La 10 mL
- RNA Assays 5 mL
- Future Use: PBMCs & Plasma 40 mL, only for qualifying Flare visits. See Section 6.3.4: *Future Use Assays*.
- Future Use: Urine 10 mL

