# Figure 8.1

The motivation for the curve in Figure 8.1 comes from the test of non-inferiority with the following hypotheses:

*H*0: the increase in risk with withdrawal of MMF (T)  $\ge a$ , and *H*A: the increase in risk with withdrawal of MMF (T) < a, where a is some value for the acceptable increase in risk.

The H0 hypothesis would be rejected in favor of HA if the upper  $(1-\alpha)$  % confident limit about the estimated risk difference (i.e. risk\_MMFwithdrawal - risk\_MMF maintenance) is less than **a**. Then, we could conclude that **T** < **a** with  $(1-\alpha)$ % confidence. Physicians and patients who are comfortable with both a risk increase of no more than **a** and a confidence level of  $(1-\alpha)$ % could conclude that withdrawal from MMF is "not unacceptably worse" than maintenance on MMF.

Recognizing that the appropriate value of a will be highly variable among physicians and patients, a single hypothesis is not defined for this study. Alternatively the upper 1-sided (1- $\alpha$ )% confidence limit (UCL) for the observed risk difference will be computed for values of  $\alpha$  ranging from 0.01 to 0.99. Note that for a given value of  $\alpha$ , the computed UCL equals the value of a, at which a null hypothesis could be rejected with a Type I error rate of  $\alpha$ . Results of these computations will be tabulated and plotted as shown in Figure 8.1.

These analyses will be completed on the mITT population.

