# 8.3.2.2 Secondary Analyses

All secondary analyses will be conducted in an exploratory fashion with p-values and confidence intervals presented as descriptive statistics with no adjustments for multiple comparisons. Interval estimates will be generated at the 95% confidence level. Analyses will be conducted on the mITT population and the per protocol population.

Analyses described for the primary analysis of the primary endpoint will be repeated using the per protocol population.

In addition, analysis will be conducted in a similar fashion for the secondary endpoints that are probability of experiencing an event including: any SELENA-SLEDAI\* flare by Week 60, any severe SELENA-SLEDAI\* flare by Week 60, any BILAG\* A flare by Week 60, a BILAG\* Renal A flare (for subjects with renal manifestations) by Week 60, and addition of aggressive adjunctive therapy to MMF or a change in MMF therapy to cytotoxic drug due to flare. These analyses will be conducted on the mITT and PP populations.

For the time to event endpoints (time to clinically significant disease reactivation, time to first SELENA-SLEDAI\* flare and time to first severe SELENA-SLEDAI\* flare), graphical summaries of time to event will be generated using Kaplan-Meier survival curves. The Greenwood method will be used to compute confidence intervals.

Descriptive statistics (mean, standard deviation or standard error, median, minimum, maximum and number of subjects in a group) and 95% confidence intervals will be reported for the difference between the treatment groups in cumulative steroid dose at Week 60; change in FACIT fatigue score from baseline to Weeks 24, 48, and 60; change in SF-36® PF and PCS domains from baseline to Weeks 24, 48, and 60; change in LupusQoL-US© from baseline to Weeks 24, 48, and 60, and change in SLICC/DI\* from baseline to Weeks 24, 48, and 60.

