# 7.2.3. Sensitivity and Additional Analyses of the Primary Endpoint

Sensitivity and additional analyses on the primary endpoint will include the following:

- 1. Analyses analogous to the primary will be run on the PP population.
- 2. Sensitivity analyses will be performed to assess the robustness of the conclusions under different assumptions for missing data for subjects who terminated early from the study. All subjects who have a mild/moderate or severe SELENA-SLEDAI flare at their last study visit will be re-categorized as experiencing clinically significant disease reactivation. Additional sensitivity analyses may be performed including single and multiple imputation methods.
- 3. A sensitivity analysis will be run to assess the impact of new or increased major immunosuppressive medications as the only cause of flare and therefore meeting primary endpoint. Subjects who re-start or increase a major immunosuppressive, but have no other disease activity that would categorize them as having a mild/moderate or severe flare will be categorized as not meeting primary endpoint (which requires both a SELENA-SLEDAI flare and increased immunosuppressive activity). Analyses analogous to the primary will be run for this sensitivity analysis.

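### The per-protocol set for the clinical re-runs can exclude subjects for deviations affecting only mechanistic outcomes, so exclusion may depend on whether the subject flared

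*Protocol*

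**What the plan says.** Protocol 8.2.3 and SAP 4.3 share one PP definition: adequate compliance and "no serious protocol deviations impacting the primary disease reactivation endpoint or mechanistic outcomes of the study". Both then say who decides: "A masked data review panel will evaluate deviations from the protocol". The examples listed are departures from the assigned regimen, changes in concurrent therapy, missed visits and procedures outside the visit window; SAP 4.3 adds compliance below 80%. Exclusion is discretionary: "The panel may exclude subjects with serious protocol deviations from the PP population".

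The set is then used for clinical endpoints. Protocol 8.3.2.2 states: "Analyses described for the primary analysis of the primary endpoint will be repeated using the per protocol population". SAP 7.2.3 item 1 states: "Analyses analogous to the primary will be run on the PP population". Protocol 8.3.2.2 and SAP 7.3 extend PP to the secondary flare endpoints. The mechanistic analysis sections, Protocol 8.3.3 and SAP 7.4, do not name the PP population.

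On specimens, Protocol 6.4.4.1 says "A flare visit is to occur when a subject experiences a flare", and the instruction there is "Collect the following specimens prior to beginning or increasing treatment with an increased dose of prednisone or immunomodulatory medications". It covers serum for cytokines, chemokines and autoantibodies, RNA, and the future-use samples.

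The primary analysis itself is on another set (Protocol 8.3.2.1): "These analyses will be completed on the mITT population".

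**The concern.** A per-protocol set should be selected on adherence, not on the outcome it is used to analyse. Here a deviation can leave reactivation fully observed, spoil a flare-time sample, and still remove the subject from the reactivation re-run. A subject who never flares cannot break the rule on specimens before flare treatment. Under Protocol 3.2 every primary event requires a flare plus increased therapy, so every event subject is exposed to it. Missed visits also count with no limit in time, so a subject who reactivates and then misses visits can be excluded although the endpoint is already known.

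At stake is how the PP curve is read beside the mITT curve. The confidence curve is motivated by a non-inferiority test (Protocol 8.3.2.1, SAP 7.2.2), where readers tend to treat agreement between mITT and PP as reassurance. If event subjects leave the PP set more often than others, PP could look more favourable to withdrawal for a reason unrelated to adherence.

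**Working it through.** **Inputs from the documents.** 120 subjects, 60 per arm; maintenance risk 0.05 to 0.15; increase 0.05 to 0.15; 85% one-sided confidence; acceptable increase a of 0.15 and above (Protocol 8.1, Table 8.1). SAP section 12 reports 8 of the first 80 subjects (10%) reactivating.

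**Assumption.** The documents give no PP exclusion rate, so every exclusion fraction f below is assumed.

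**Step 1: reproduce the plan's figure.** With unpooled SE, power = Φ((a − increase)/SE − z(0.85)). For 0.05 versus 0.10 and a = 0.15:
- SE = √((0.05×0.95 + 0.10×0.90)/60) = 0.0479
- (0.15 − 0.05)/0.0479 − 1.036 = 1.05, so power is 85.4%; Table 8.1 gives 85%.

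All 22 cells of Table 8.1 agree within 2 percentage points, so the same normal form is used below. Without censoring, the Kaplan-Meier risk equals the simple proportion.

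**Step 2: an attainable data set.** Take 3/60 versus 9/60, which is 12/120, the 10% pooled rate in SAP section 12. Confidence = Φ((0.15 − RD)/SE), where RD is the risk difference.

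| Event subjects dropped (maintenance, withdrawal) | RD | Confidence increase ≤ 0.15 | 85% upper limit |
|---|---|---|---|
| 0, 0 | 0.100 | 82% | 0.156 |
| 1, 2 | 7/58 − 2/59 = 0.087 | 90% | 0.137 |
| 1, 0 | 9/60 − 2/59 = 0.116 | 74% | 0.170 |

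With a score method the first two rows give 81% and 88%.

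**Step 3: equal exclusion of event subjects only.** If a fraction f of event subjects is dropped in both arms and no one else is, risk p becomes p(1 − f)/(1 − pf). For 0.05 versus 0.15, RD 0.100 becomes 0.092, 0.083 and 0.074 at f = 10%, 20% and 30%. Over the six Table 8.1 risk pairs, RD falls to 0.91–0.94, 0.82–0.88 and 0.73–0.81 of its value.

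**Step 4: relax that assumption.**
- Events and non-events dropped at the same rate: RD stays at 0.100.
- 20% of events and 30% of non-events dropped: 0.12/0.715 − 0.04/0.705 = 0.168 − 0.057 = 0.111, so RD rises.
- 20% of events dropped in one arm only: 0.074 if withdrawal, 0.110 if maintenance.
- 20% of all flaring subjects dropped, taking events as 40% of flaring subjects (a proxy from the treated-flare share in Protocol 1.5): 0.05 versus 0.15 goes from 0.100 to 0.089, but 0.15 versus 0.30 goes from 0.150 to 0.153.

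**The case against.** The strongest reply is that nothing here is automatic. Exclusion needs a serious deviation and a decision by a masked panel. No text classes a late or missed flare specimen as serious, and specimen timing is not among the listed examples. That stands. But the documents do not say what the panel is masked to, and a flare-specimen deviation itself reveals a flare, so masking to arm would not remove the dependence on outcome.

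The specimen route is also narrow. PBMC, urine and extra plasma are future-use samples, outside the Protocol 3.3.3 assessments. C3, C4 and anti-dsDNA are outside the pre-treatment instruction, and the planned autoantibody comparison needs only Baseline and Week 60. Cytokine, chemokine and RNA samples remain, and those are due at every scheduled visit from every subject, so non-event subjects can also be excluded. This stands, and it is why the direction is open.

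There are partial cut-offs already. Protocol 5.6 exempts prohibited medication once the endpoint is met, and SAP 6.2 counts compliance only while study-provided MMF is taken. Visits missed, or procedures done out of window, after the event have no such limit.

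The SAP synopsis says in general terms that secondary analyses use PP as well. If that is meant to cover mechanistic analyses, it supports a separate set for them, not a shared one.

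A reader might infer that the PP re-run will remove events selectively, that the risk difference will shrink, and that PP will cross an 85% decision line. The documents do not support this. They give no exclusion rate; Step 4 shows RD can rise; and the 85% is a sample-size assumption about what physicians would want, not a PP threshold. Nor do they make PP the deciding check: it is one supportive analysis in a plan described as descriptive.

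**Conclusion.** The concern holds in a limited form. The plan permits deviations relevant only to mechanistic outcomes, and visits missed after the event, to remove subjects with a known reactivation status from the supportive clinical re-runs. Exclusion from PP may therefore depend on outcome.

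PP would look more reassuring about withdrawal if event subjects were dropped more often than non-event subjects, at similar rates in both arms or more often in the withdrawal arm. Other patterns leave RD unchanged or raise it. With about 12 events, three exclusions are enough to change the picture, as Step 2 shows, but that example is illustrative: its counts are chosen and it starts just below 85%. The mITT primary result is unaffected, and SAP 6.1 confirms that no deviation removes a subject from mITT. The change is worth making because it is cheap and closes an avoidable route to bias.

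**What to change.** In Protocol 8.2.3 and SAP 4.3:
- Delete the reference to mechanistic outcomes from the PP definition used for clinical endpoints.
- If the mechanistic analyses need a restricted set, define a separate mechanistic-evaluable population and name it in SAP 7.4.
- State that, for reactivation, only deviations dated before the subject's reactivation date (as SAP 7.2.1 defines it) can exclude.
- Report PP exclusions by arm, reason and event status, and say what the panel is masked to.

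The cost is wording and one extra population flag, with no new data. The downside is two evaluable sets to report instead of one. The date cut-off also leaves non-event subjects with a longer period in which a deviation can exclude them; the table by event status would show whether that matters.
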